3.2 Exclusion Criteria

- 3.2.1 Prior liver transplant.
- 3.2.2 Prior systemic therapy directed at advanced or metastatic HCC.
- 3.2.3 Prior immunotherapy with IL-2, or anti-PD-1, anti-PD-L1, or anti-cytotoxic T-lymphocyte-associated antigen-4 (CTLA-4) antibody, or any other antibody or drug specifically targeting T-cell co-stimulation or immune checkpoint pathways.
- 3.2.4 Prior therapy with axitinib or any prior therapies with other VEGF pathway inhibitors.
- 3.2.5 Clinically significant, uncontrolled heart disease and/or recent events including any of the following:
 - 3.2.5.1 History of acute coronary syndromes (including myocardial infarction, unstable angina, coronary artery bypass grafting, coronary angioplasty, or stenting) or symptomatic pericarditis within 12 months prior to screening).
 - 3.2.5.2 History of documented congestive heart failure (New York Heart Association functional classification III-IV).
 - 3.2.5.3 History of cerebrovascular accident, transient ischemic attack, deep vein thrombosis, or pulmonary embolism within 6 months of screening.
 - 3.2.5.4 Patient has a left ventricular ejection fraction <40% as determined by MUGA scan or ECHO (MUGA and ECHO are not required prior to enrollment).
- 3.2.6 Known human immunodeficiency virus (HIV) positive (testing not required).
- 3.2.7 History of cerebrovascular accident, transient ischemic attack, or thromboembolic events (including both pulmonary embolism and deep venous thrombus but not including tumor thrombus) within the last 6 months.
- 3.2.8 Hypersensitivity to IV contrast; not suitable for pre-medication.
- 3.2.9 Active or fungal infections requiring systemic treatment within 7 days prior to screening.
- 3.2.10 Known history of, or any evidence of, interstitial lung disease or active noninfectious pneumonitis.
- 3.2.11 Evidence of poorly controlled hypertension which is defined as systolic blood pressure >159 mmHg or diastolic pressure >99 mmHg despite optimal medical management.

- 3.2.12 Pre-existing thyroid abnormality with thyroid function that cannot be maintained in the normal range with medication.
- 3.2.13 Active, known, or suspected autoimmune disease with the exception of subjects with vitiligo, type I diabetes mellitus, resolved childhood asthma or atopy. Subjects with suspected autoimmune thyroid disorders may be enrolled if they are currently euthyroid or with residual hypothyroidism requiring only hormone replacement. Subjects with psoriasis requiring systemic therapy must be excluded from enrollment.
- 3.2.14 Patient has any other concurrent severe and/or uncontrolled medical condition that would, in the investigator's judgment, cause unacceptable safety risks, contraindicate patient participation in the study or compromise compliance with the protocol (e.g. chronic pancreatitis, active untreated or uncontrolled fungal, bacterial, or viral infections, etc.).
- 3.2.15 Known history of active bacillus tuberculosis.
- 3.2.16 Subjects with a condition requiring systemic treatment with either corticosteroids (> 10 mg/day prednisone equivalent) or other immunosuppressive medications within 14 days of study administration. Inhaled or topical steroids and adrenal replacement doses >10 mg/day prednisone equivalents are permitted in the absence of autoimmune disease.
- 3.2.17 Patient who has received definitive radiotherapy with the sole intent of disease control \leq 4 weeks prior to study entry. Palliative radiotherapy for symptomatic control (such as to bone metastases) is acceptable (if completed at least 2 weeks prior to study drug administration and no additional radiotherapy for the same lesion is planned).
- 3.2.18 Patient has had major surgery within 14 days prior to starting study drug or has not recovered from major side effects (tumor biopsy is not considered as major surgery).
- 3.2.19 Clinically apparent ascites on physical examination, ascites present on imaging studies is allowed.
- 3.2.20 Known severe hypersensitivity reactions to monoclonal antibodies (Grade 3).
- 3.2.21 Active gastrointestinal bleeding within previous 2 months.
- 3.2.22 History of any condition requiring anti-platelet therapy (aspirin >300 mg/day, clopidogrel >75 mg/day).
- 3.2.23 Diagnosis of any other malignancy within 5 years prior to screening visit, except for adequately treated basal cell or squamous cell skin cancer, or carcinoma in situ of the breast or of the cervix, or low-grade (Gleason 6 or below) prostate cancer on surveillance with no plans for treatment intervention (eg, surgery, radiation, or castration).
- 3.2.24 Prisoners or subjects who are involuntarily incarcerated.
- 3.2.25 History of leptomeningeal disease.
- 3.2.26 Symptomatic or clinically active brain metastases.

- 3.2.27 Pregnant or nursing (lactating) women, where pregnancy is defined as the state of a female after contraception and until the termination of gestation, confirmed by a positive hCG laboratory test.
- 3.2.28 Has dual active HBV infection (HBsAg (+) and /or detectable HBV DNA) and HCV infection (anti-HCV Ab(+) and detectable HCV RNA) at study entry.
- 3.2.29 Known prior or suspected hypersensitivity to study drugs or any component in their formulations.
- 3.2.30 Current use or anticipated need for drugs that are known strong CYP3A4/5 inducers, including their administration within 10 days prior to patient receiving the first study treatment, eg, phenobarbital, rifampin, phenytoin, carbamazepine, rifabutin, rifapentin, clevidipine, St John's wort.
- 3.2.31 Patients with 2+ proteinuria on urine dipstick analysis and confirmed to have ≥ 2 grams of protein in a 24-hour urine collection.
- 3.2.32 Current use or anticipated need for treatment with drugs or foods that are known strong CYP3A4/5 inhibitors, including their administration within 10 days prior to patient receiving the first study treatment, (eg, grapefruit juice or grapefruit/grapefruit-related citrus fruits, ketoconazole, miconazole, itraconazole, voriconazole, posaconazole, clarithromycin, telithromycin, indinavir, saquinavir, ritonavir, nelfinavir, amprenavir, fosamprenavir, nefazodone, lopinavir, troleandomycin, mibefradil, and conivaptan). The topical use of these medications (if applicable), such as 2% ketoconazole cream, is allowed.

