3.0 SUBJECT ELIGIBILITY

Eligibility waivers are not permitted. Subjects must meet all of the inclusion and exclusion criteria to be registered to the study. Study treatment may not begin until a subject is registered.

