	3-4	Hold until symptoms resolve to baseline or until Grade ≤ 1 . Then, reduce by 1 dose level.
Hematologic abnormalities	1-3	Continue at same dose level.

	4	Hold until symptoms resolve to baseline or until Grade ≤1. Restart axitinib dose reduced by 1 dose level. Note: Grade 4 lymphopenia not associated with clinical events, (e.g, opportunistic infection) may continue on with axitinib.
Stevens-Johnson syndrome	3-4	Permanently discontinue.
Other non-hematologic toxicities and laboratory abnormalities	1-2	Continue at same dose level.
	3	Hold until symptoms resolve to baseline or until Grade ≤2. For toxicities controlled with symptomatic medications or asymptomatic laboratory abnormalities, continue at the same dose level or reduce by 1 dose level as per investigator judgment. For all other toxicities, reduce by 1 dose level.
	4	Hold until symptoms resolve to baseline or until Grade ≤2. Then, reduce by 1 dose level as per investigator judgment. Permanently discontinue axitinib for Grade 4 toxicities that meet any of the following conditions: 1) recurrent 2) life-threatening 3) reversible posterior leukoencephalopathy syndrome 4) arterial thrombosis/ischemia

4.2.4 Infusion related reactions.

Because avelumab and bavituximab are administered as infusions, infusion reactions are possible and may include symptoms such as fever, chills, shortness of breath, headache, and rigors. Infusion modifications depend on the severity of reactions as detailed in Table 4 below.

Table 4. Infusion-related reactions caused by avelumab or bavituximab.

NCI CTCAE Grade	Infusion modifications
1	Decrease the avelumab and/or bavituximab infusion rate by 50%.
2	Temporarily discontinue avelumab and/or bavituximab infusion. Resume infusion at 50% of previous rate once infusion-related reaction has resolved or decreased to at least Grade 1 in severity, and monitor closely for any worsening.
3-4	Stop the infusion immediately and disconnect infusion tubing from the patient. Patients may not receive further treatment.

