5.1.4 Review subject eligibility criteria

Eligibility will be determined according to the inclusion/exclusion criteria as described in Section 3.

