7.3 Baviximab

7.3.1 Contraindications

Known allergy or hypersensitivity to any component of the drug product or prior Grade ≥ 3 infusion reaction, hypersensitivity, or anaphylaxis after receiving any other monoclonal antibody therapy.

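### Exclusion 3.2.20 omits prior severe infusion reactions, which Section 7.3.1 lists as a contraindication to bavituximab

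*Combined protocol and SAP*

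**What the plan says.** Three places in the combined protocol and SAP bear on this.

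- **Section 3.2.20** is the only exclusion concerning reactions to antibodies other than the study drugs: "Known severe hypersensitivity reactions to monoclonal antibodies (Grade 3".
- **Section 7.3.1** gives the bavituximab contraindications. One is allergy or hypersensitivity to a component of the product. The other is a prior Grade 3 or higher "infusion reaction, hypersensitivity, or anaphylaxis after receiving any other monoclonal antibody therapy".
- **Sections 3.0 and 5.1.4** make Section 3 the test for entry. Section 3.0 says "Subjects must meet all of the inclusion and exclusion criteria to be registered to the study", and Section 5.1.4 says "Eligibility will be determined according to the inclusion/exclusion criteria as described in Section 3". Neither refers to the contraindications in Section 7.

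Bavituximab is the only one of the three drugs with a listed contraindication: Sections 7.1.1 (axitinib) and 7.2.1 (avelumab) both say there are none.

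**The concern.** The contraindication names three kinds of event and the exclusion names one. A patient with a prior Grade 3 or higher infusion reaction to another antibody falls under 7.3.1 but not under the literal wording of 3.2.20. Such a patient can pass the eligibility check, and the only remaining protection is that someone consults Section 7.3.1 before the first infusion.

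The matter at stake is patient safety, not inference. Every patient is assigned bavituximab weekly, and on shared days it is infused before avelumab (Sections 4.1.3 and 4.1.7). The required diphenhydramine and acetaminophen premedication is tied to avelumab, and the regimen table lists none for bavituximab. A patient admitted through this gap would receive the contraindicated antibody first, with no required premedication.

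**Working it through.** No arithmetic is involved beyond counting criteria. The check compares the two texts and then asks whether anything else in Section 3 closes the gap.

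**Step 1. Compare the exclusion with the contraindication.**

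| Element | 3.2.20 (exclusion) | 7.3.1 (contraindication) |
|---|---|---|
| Prior infusion reaction | Not named | Named |
| Prior hypersensitivity | Named | Named |
| Prior anaphylaxis | Not named; falls under severe hypersensitivity on an ordinary reading | Named |
| Grade | 3 | 3 or higher |
| Causative agent | Monoclonal antibodies | Any other monoclonal antibody |

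The substantive gap is the infusion reaction. There is also a lesser one in the grade: taken literally, Grade 4 is not named in 3.2.20.

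**Step 2. Look for another criterion that covers the case.** Section 3 has 13 inclusion criteria (3.1.1 to 3.1.13) and 32 exclusion criteria (3.2.1 to 3.2.32), and 13 + 32 = 45.

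- Criteria naming an infusion reaction: 0.
- Criteria naming hypersensitivity: 3. These are 3.2.8 (IV contrast), 3.2.20 (monoclonal antibodies) and 3.2.29 (study drugs).
- 3.2.29 reads "Known prior or suspected hypersensitivity to study drugs or any component in their formulations". It matches the first half of 7.3.1 but does not reach reactions to other antibodies.
- 3.2.14 begins "Patient has any other concurrent severe and/or uncontrolled medical condition that would" and depends on investigator judgment. A past reaction is not a concurrent condition, so it does not close the gap.

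**Step 3. Ask whether the two terms are interchangeable in this protocol.** They are not treated that way. Section 7.3.1 lists infusion reaction and hypersensitivity as separate items. Section 4.2.4 gives infusion reactions their own grading table and says that "infusion reactions are possible and may include symptoms such as fever, chills, shortness of breath, headache, and rigors". A past event with that picture could well have been recorded as an infusion reaction only. The terms do overlap: Section 7.3.2 includes wheezing and urticaria among the signs of a bavituximab infusion reaction.

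**Step 4. Follow a patient through the written process.** Take a prior Grade 3 infusion reaction to an antibody other than the study drugs, recorded under that name. On the literal text, 3.2.20, 3.2.29 and 3.2.14 do not apply. If all else is met, the patient is eligible under 5.1.4 and can be registered under 3.0, although 7.3.1 contraindicates bavituximab.

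**Step 5. Judge how many patients could be affected.** The documents give no frequency of prior antibody exposure or reactions, so no rate can be calculated. Several exclusions make exposure uncommon: prior systemic therapy for advanced or metastatic HCC (3.2.2), checkpoint antibodies and similar immunotherapy (3.2.3), VEGF pathway inhibitors (3.2.4), most autoimmune disease (3.2.13), recent immunosuppression (3.2.16) and most other recent malignancy (3.2.23). They do not remove it. For example, 3.2.23 looks back 5 years and 3.2.16 looks back 14 days.

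**The case against.** The strongest reply is that this is a matter of terminology with little practical effect. The signs of a severe infusion reaction and of hypersensitivity overlap heavily, and a cautious investigator would apply 3.2.20 to both. Section 4.2.4 describes reactions on study and does not show how earlier reactions to other drugs were recorded, so the failure path is inferred. Section 7.3.1 is itself protocol text, and Section 11.5 requires the study to be run as the protocol describes, so dosing against it would be a departure even for a registered patient. Screening takes a full medical history and reviews previous medications (5.1.2 and 5.1.5). A Grade 3 or 4 reaction on study stops the infusion and bars further treatment (Table 4).

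Much of this stands as a limit on size. The broad reading is plausible, the prohibition in 7.3.1 has not disappeared, and there may be no affected patient. It does not remove the conflict. The broad reading is optional, the history is not checked against any criterion that names infusion reactions, and the on-study rules act only after the patient has reacted. A contraindication the protocol itself states should be applied before registration.

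**Conclusion.** The concern holds. Read literally, Section 3 can admit a patient to whom Section 7.3.1 says bavituximab should not be given, and no other criterion prevents it. The effect is confined to few patients, possibly none, of up to 29 evaluable, with no consequence for type I error, power or sample size.

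The conclusion assumes that sites apply the criteria as written and that some past severe reactions are recorded as infusion reactions without being called hypersensitivity. Where a site reads 3.2.20 broadly or checks 7.3.1 before registration, the gap has no effect. It should be corrected because it concerns safety and is almost free to close; it does not threaten the trial's conclusions.

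**What to change.** Replace 3.2.20 with wording that carries the full contraindication, for example: *Any previous reaction of Grade 3 or higher to a monoclonal antibody, whether recorded as an infusion reaction, as hypersensitivity or as anaphylaxis.* This brings in infusion reactions and settles the grade at 3 or higher. Exclusion 3.2.29 can stay as it is.

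The cost is one amended eligibility line and at most an occasional screen failure. No statistical section needs to change.

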4.0 TREATMENT PLAN

4.1 Treatment Dosage and Administration

- 4.1.1 For the purpose of this study, the investigational products are avelumab, axitinib, and bavituximab. All investigational drugs will be administered on an outpatient basis.
- 4.1.2 Avelumab dosage form and packaging: Avelumab is a sterile, clear, and colorless solution intended for IV administration. Avelumab is formulated as a 20.0 mg/mL solution and will be supplied by Pfizer in single-use glass vials, stoppered with a rubber septum and sealed with an aluminum polypropylene flip-off seal. Avelumab will be dosed at the investigational site. For application in this trial, avelumab drug product must be diluted with 0.9% saline solution (sodium chloride injection).
- 4.1.3 Avelumab administration: Avelumab will be administered as a 1-hour IV infusion on Day 1 and Day 15 of each 28-day cycle. Avelumab may be administered up to 3 days before or after the scheduled Day 1 of each dose due to administrative reasons. Avelumab should be administered at least 30 minutes after the bavituximab infusion (on days when both are administered). In order to mitigate infusion-related reactions, a required premedication regimen of 25 to 50 mg IV or oral equivalent diphenhydramine and 650 mg IV or oral equivalent acetaminophen will be administered immediately prior to administration of avelumab for the first 4 infusions of avelumab. Premedication should be administered for subsequent avelumab doses based upon clinical judgment and presence/severity of prior infusion reactions. Sites should make every effort to target infusion timing to be as close to 1 hour as possible (no longer than 2 hours).

The dose amount required to prepare the avelumab infusion solution will be based on the patient's weight in kilograms (kg). All patients should be weighed within 7 days prior to dosing for every cycle. If the patient experienced either a weight loss or gain >10% compared to the weight used to calculate the prior dose, the amount of study drug required for preparation and administration for the current cycle must be recalculated using this most recent weight obtained. The maximum dose is 2000 mg for all adult patients. Avelumab dose reduction for toxicity management is not permitted, however next cycle administration may be omitted due to persisting toxicity.

- 4.1.4 Axitinib dosage form and packaging: Axitinib will be supplied by Pfizer as 1 mg and 5 mg film-coated tablets for oral administration in light-resistant high-density polyethylene (HDPE) bottles with desiccant.
- 4.1.5 Axitinib administration: Axitinib will be provided in quantities appropriate for the study visit schedule. A qualified staff member will provide the study treatment via a unique container number. Axitinib will be dispensed every 4 weeks or as otherwise indicated.

Axitinib will be administered orally BID at approximately the same time in the morning and evening on a continuous dosing schedule. Axitinib tablets are to be taken approximately 12 hours apart and may be administered without regard to meals or avelumab and bavituximab administration. Tablets must not be crushed, split, or dissolved, and patients should be instructed to swallow the study medication whole without manipulation or chewing of the medication prior to swallowing.

Patients must be instructed that if they miss a dose or vomit any time after taking a dose, they must not "make it up" with an extra dose, but instead resume subsequent doses as prescribed. Any missed dose may be taken late, up to 3 hours, before the next scheduled dose of that day, otherwise, it should be skipped and dosing resumed with subsequent doses as prescribed. Patient must be instructed to record all doses (missed or vomited doses or extra doses) in a dosing diary supplied by the site.

- 4.1.6 Bavituximab dosage form and packaging: Bavituximab is supplied OncXerna as a sterile, preservative-free solution with 10 mM acetate at pH 5.0 and diluted with 0.9% saline (normal saline) to a final volume of 100 mL.
- 4.1.7 Bavituximab administration: Bavituximab will be administered weekly on Days 1, 8, 15 and 22 of the 28-day cycle.

Infusion preparation and administration are to be performed as follows:

1. Draw up the volume of a vial using a sterile syringe attached to an appropriate needle (a vented spike or other appropriate transfer device may be used). Fill treatment into a sterile glass bottle or plastic IV bag.
2. Using aseptic techniques, repeat procedure until the calculated volume has been put into the container. Bring the final volume to 100 mL using 0.9% Sodium Chloride Injection, USP.
3. Administer through a low protein binding 0.2-micrometer in-line filter (placed as proximal to the patient as practical).
4. Affix the infusion line and prime it with infusate before starting the infusion. Infuse the solution intravenously over 90 (\pm 10) minutes. No reduction in infusion time will be permitted. Flush the line with normal saline after infusion.

REGIMEN DESCRIPTION

Agent	Premedications; Precautions	Dose	Route	Schedule	Cycle Length
Bavituximab		3 mg/kg in NS	IV over 90 min	Days 1, 8, 15, 22	4 weeks (28 days)
Avelumab	Premedicate with diphenhydramine and acetaminophen prior to avelumab.	10 mg/kg in NS (maximum dose is 2000 mg)	IV over 60 min at least 30 min after bavituximab	Days 1, 15	
Axitinib		5 mg tablet	PO BID	Daily	

4.2 Safety Lead-in, Toxicities, and Dosing Delays/Dose Modifications

Any subject who receives treatment on this protocol will be evaluable for toxicity. Each patient will be assessed for the development of toxicity according to the Time and Events table (Section 5.3). Toxicity will be assessed according to the NCI Common Toxicity Criteria for Adverse Events (CTCAE), version 5.0.

4.2.1 Safety Lead-in and Dose-limiting Toxicities

A safety and tolerability assessment will be performed for patients treated with axitinib, bavituximab, and avelumab after the first 6 patients evaluable for dose-limiting toxicities have completed 1 cycle (ie, Cycle 1 Day 28). Patients will be considered evaluable for dose-limiting toxicities assessment if they have completed all scheduled study visits during the first cycle and have received 2 (100%) of the 2 planned doses of avelumab and at least 3 (75%) of the 4 planned doses of bavituximab in Cycle 1.

Dose-limiting toxicities are defined as any Grade 3 or greater AE that occurs during the first cycle (28 days) and are considered to be related (possible, probable, or definite) to study drug, specifying attribution to axitinib, avelumab, bavituximab, or all drugs. Intolerable Grade 2 gastrointestinal toxicities (such as persistent nausea/vomiting or diarrhea) will also be considered dose-limiting toxicities if they are considered to be related to any study drug. See Tables 2 and 3 below and Section 7.0 for AEs associated with axitinib, avelumab, or bavituximab.

Enrollment of additional patients after the first 6 potentially evaluable patients for dose limiting toxicities will be suspended until after assessment of the safety lead-in phase by the UTSW Simmons Cancer Center Gastrointestinal Disease-Oriented Teams (GI DOT) is complete.

- If ≤ 1 dose-limiting toxicity occurs, trial enrollment will proceed without any modifications.
- If ≥ 2 dose-limiting toxicities occurs, all treatment-related AEs will be reviewed by the GI DOT for consideration of modification or termination of the study. Modifications may include reducing the starting dose of axitinib by one dose level to 3 mg BID for all subsequent patients enrolled and not permitting dose re-escalation above dose level 0.

